A feasibility clinical trial conducted by our group tested the ReCognitionVR cognitive interventions on older and young healthy volunteers (Appendix A. Final Study Report). The results of this study showed that ReCognitionVR-based cognitive exercises were feasible, acceptable, and tolerable by older healthy subjects. In stage 2 of our research study, we want to evaluate the safety, feasibility, acceptability, and tolerability of VR-based cognitive exercises in 60-year-old or older patients following abdominal surgery admitted to the surgical floor at Houston Methodist Hospital (HMH). Our premise is that VR-based cognitive stimulation software will allow the controlled delivery of structured cognitive exercises focusing on orientation, attention, memory, and executive functions. The system will allow customized frequency and duration of cognitive exercises based on the users' difficulty level in a delightfully relaxed-environment with beach wave sounds.

Hypothesis:

We will test the hypothesis that the test population will find ReCognitionVR-based cognitive exercise safe, feasible, acceptable, and tolerable.

2. Purpose of the Study / Objectives

This study aims to assess the feasibility, acceptability, and safety of using ReCognitionVR-based software in older surgical patients. Results from this study will be used to inform the design of a future study in critically ill hospitalized patients at risk for delirium.

The question that drives this study is:

In surgical floor patients, what is the safety and feasibility of using the ReCognition VR-based cognitive exercise, and what is the acceptability and tolerability of the exercise?

OBJECTIVES AND ENDPOINTS

OBJECTIVES	ENDPOINTS	JUSTIFICATION FOR ENDPOINTS
Primary		
The primary objective of this study is the safety of VR-based cognitive stimulation exercises for older surgical patients.	The primary endpoint is the proportion of treatment-emergent adverse events (TEAE) in each group (experimental and control).	 To assess tolerability of ReCognitionVR-based cognitive stimulation exercises. Adverse events (e.g., cybersickness) will assess tolerability

Page 2 of 21

OBJECTIVES	ENDPOINTS	JUSTIFICATION FOR ENDPOINTS
		during engagement through exercise provided by ReCognitionVR games.
Secondary		

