- Motion Sensor
- Flat Screen TV with Software

The VR headsets manufactured by the Oculus Quest 2 glasses (Facebook Inc., USA) with stereoscopic vision and stereo sound will be used to show the VR to study participants. After headset placement, the study participants will be able to follow instructions provided by virtual nurse AVATAR. The participants will receive low cognitive load exercises based on virtual reality techniques, including a relaxed environment, music therapy, time orientation, delivery instructions, and task completion motivation. The exercise task will focus on attention, organized thinking, and motor activities.

9. If you are in the traditional orientation method, you will be visited by a nurse at the start of each nursing shift. The nurse will ask you questions to check your memory and attention. Examples of questions include asking you for your name, the date, where you are, and what just happened to you. This will be repeated during every nurse shift change and is the usual care you would receive, even if you were not in the study. In this method, your vital signs (oxygen levels, how fast you are breathing, and your blood pressure) will be measured at different time points after your abdominal surgery as part of your standard care. When you wake up from surgery, you will have the traditional orientation questions asked of you until you are discharged from the hospital. Your participation in this study will be over after you leave the hospital.

Schedule of Activities

Procedures	Screening*	Day 1,	Day 1,	Day 1,	Day 1,	Post 24	Post 48	Post 72
		Time 1:	Time 2:	Time	Time	hours	hours	hours
		pre	10	3: post	4: end			
			minutes		of			
					study			
Visit number	Visit 0 or 1	Visit 1				Visit 2	Visit 3	Visit 4
Informed	X							
consent								
Demographics	X							
Medical history	X							
Randomization		X						
Administer			X-					
study								
intervention								
Concomitant	X							
medication								
review								

Page 9 of 21

Procedures	Screening*	Day 1, Time 1: pre	Day 1, Time 2: 10 minutes	Day 1, Time 3: post	Day 1, Time 4: end of study	Post 24 hours	Post 48 hours	Post 72 hours
Visit number	Visit 0 or 1	Visit 1				Visit 2	Visit 3	Visit 4
Physical exam (including height and weight)	X							
Frailty screening assessment	X							
Mini-Cog screening assessment	Х							
RASS Score	Х							
Pulse oximetry		X	Х	Х				
Respiratory rate		Х	Χ	Х				
Blood pressure		Х	Χ	Х				
System User Survey					Х			

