All data obtained for the study will be stored in a password-protected spreadsheet on a Methodist server and will only be accessible to IRB-approved investigators and research staff at Houston Methodist. Data will be completely de-identified at the time of collection and sent to the statistician via secure mail for analysis. Research materials will be stored in a password-protected computer system database on a secure server on the Houston Methodist network. Data collected will be transferred and stored on REDCap®, a secure web application for building and managing databases. Study personnel requiring access will have their Login/Password assigned to the project. Access to clinical study information will be based on individuals' roles and responsibilities. All study data will be transmitted over an encrypted SSL (Secure Sockets Layer) connection that requires user authentication. This application is designed to be in full compliance with the International Conference on Harmonization and Good Clinical Practices

Page 11 of 21

(ICH-GCP), the FDA's Code of Federal Regulations (CFR) 21 Part 11 Electronic Record and Electronic Signatures, the FDA's "Guidance: Computerized Systems Used in Clinical Trials," and the Privacy Rule of the Health Insurance Portability and Accountability Act of 1996 (HIPAA).

Houston Methodist Research Institute (HMRI) policy on record retention will be followed, and human subject research data will be kept for a minimum of 6 years after completing the study. Research written materials will be stored in the Department of Surgery Research Office (Skurlock 1150) and electronic materials on password-protected computer systems on a secure server on the Houston Methodist network.

A unique identification code will be assigned to each participant in this study, and the study team will maintain the linking log with the study files. The only individuals who can see un-coded personal health information include the Study Team and the Institutional Review Board at the hospital, employees of the sponsor who check that this study is being done correctly, and regulatory authorities where required by law.

Data to be collected include:

- Sex
- Age
- Race, ethnicity
- Height, weight
- SpO2 (Time Frame: before, during, and after use of ReCognitionVR software; see Schedule of Activities)
- Respiratory rate (Time Frame: before, during, and after use of ReCognitionVR software; see Schedule of Activities)

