Only the minimum amount of personal information needed to conduct this study will be collected regarding participants' privacy interests. Study participants will be informed that the only individuals who can see un-coded personal health information include the following: the Study Doctor, other employees who work on this study (including the Institutional Review Board) at the hospital, employees of the sponsor who check that this study is being done correctly, and

Page 14 of 21

regulatory authorities where required by law. In addition, participants will be carefully informed about the Release of Health Information section in the Informed Consent Form (ICF), which describes who will access their information and how it will be used. We will emphasize that participation in this study is voluntary and that participants can choose at any time to cease participation and revoke authorization to use and disclose their information.

14. Risks to Subjects

The risks below are associated with the use of the Oculus Quest 2 VR Headset Device.

All adverse events (AEs) will be captured and recorded at each time point. We will report AEs as a proportion of study participants who developed AEs.

Specific AEs to be monitored will include:

Neurological AEs: (Cybersickness is defined as new-onset blurry vision, double vision, dizziness, headaches, eye fatigue, drowsiness, disorientation, and apathy) within 5 minutes after starting the study intervention).

Cardiac Adverse Events: New-onset hypotension (SBP <90 mmHg and DBP <60 mmHg), Bradycardia (HR < 50), Tachycardia (HR> 100), and Arrhythmias (Supraventricular or ventricular) with HR> 150 beats per minutes within 5 minutes after the starting of 3D Simulated VR sessions. Or changes >20% from baselines.

Pulmonary Adverse Events: New-onset hypoxia: SpO2 < 88%, Respirator rate > 35 breaths/minute within 5 minutes after starting 3D Simulated VR sessions.

The safety precautions to minimize the risk to participants are as follows:

- *Vital signs BP*, HR, RR, SPO2, and pain scores (using numeric pain rating scale tool) will be monitored before, during, and after using ReCognitionVR software.

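### Three of the four cardiac adverse events in Section 14 are defined by heart rate, but the Schedule has no heart-rate row and none is specified for controls

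*Combined protocol and SAP*

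**What the plan says.** The objectives table in Section 2 states: "The primary endpoint is the proportion of treatment-emergent adverse events (TEAE) in each group (experimental and control". Section 14 adds that adverse events are reported as the proportion of participants who develop one.

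Section 14 names four cardiac events. One is defined by blood pressure: "New-onset hypotension (SBP <90 mmHg and DBP <60 mmHg". The other three carry a heart-rate threshold: "Bradycardia (HR < 50), Tachycardia (HR> 100", and arrhythmia, of either supraventricular or ventricular type, at a rate above 150. The list is tied to the first 5 minutes after the VR session starts and is followed by a relative criterion, "Or changes >20% from baselines". Under safety precautions, the same section says that blood pressure, heart rate, respiratory rate, SpO2 and pain scores "will be monitored before, during, and after using ReCognitionVR software".

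The Schedule of Activities in Section 5 lists "Pulse oximetry", respiratory rate and blood pressure at Time 1 (pre), Time 2 (10 minutes) and Time 3 (post). It has no heart-rate row. An adverse event review is scheduled at all four Day 1 times and at 24, 48 and 72 hours.

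The control-arm description in Section 5 names three vital signs, taken at various times after surgery as part of usual care: oxygen level, breathing rate and blood pressure.

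**The concern.** A threshold event such as a heart rate above 100 may cause no symptoms, so it is recognised only if heart rate is measured. The relative criterion, if it applies to heart rate, also needs a recorded baseline. The only sentence that commits to measuring heart rate is a safety precaution tied to use of the VR software. It does not say that values are recorded, and it does not reach the control arm.

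The primary endpoint is reported for both arms. If one arm has its heart rate watched around a supervised session and the other has no specified measurement, a difference in event proportions could reflect how closely participants were observed, not what happened to them. The study is meant to inform a larger trial, so its safety proportions will be carried forward.

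**Working it through.** The plan gives no figure to reproduce. The check sets the sections side by side.

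**1. Which cardiac events need heart rate.** Of the four named in Section 14, hypotension uses blood pressure; bradycardia (<50), tachycardia (>100) and arrhythmia (>150) use heart rate. That is 3 of 4.

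**2. Where heart rate appears.**

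| Place | Vital signs named | Heart rate? |
|---|---|---|
| Section 2, secondary endpoints | SpO2, RR, BP | No |
| Section 4, safety measures | SpO2, RR, BP | No |
| Section 5, Schedule | Oximetry, RR, BP | No |
| Section 5, control-arm description | Oxygen, breathing rate, BP | No |
| Section 8, data list | SpO2, RR | No |
| Section 14, safety precautions | BP, HR, RR, SpO2 | Yes, around VR use |

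The Section 8 list carries little weight. It includes "Respiratory rate (Time Frame: before, during, and after use of ReCognitionVR software; see Schedule of Activities" but omits blood pressure, which the Schedule does collect, so it is not exhaustive. The Schedule and the control-arm text are the stronger evidence.

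**3. What each arm would yield if the plan is followed as written.**
- VR arm: heart rate is monitored, and a recognised event can be entered at an adverse event review. No scheduled value exists from which to derive or check it.
- Control arm: the adverse event review also applies, but no section specifies a heart-rate measurement that would bring an event to it.

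**4. Timing.** The window closes 5 minutes after VR start. The scheduled readings are before the session, at 10 minutes and after it. None is fixed between 0 and 5 minutes, and this is as true of blood pressure as of heart rate. Controls have no VR start, so neither the 5-minute window nor the 10-minute reading has a stated origin for them.

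**5. Leverage of a missed event.** With n = 15 per arm (Section 4), and counting participants with at least one event, failing to count k participants who have no other event lowers the arm's proportion by k/15:
- k = 1: 1/15 = 6.7 percentage points
- k = 2: 2/15 = 13.3 percentage points
- k = 3: 3/15 = 20.0 percentage points

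The documents give no basis for choosing k. These values show sensitivity; they do not estimate bias.

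**6. Do measured vital signs produce adverse events in this programme?** Yes. In the preliminary study summarised in Section 3, one of the four adverse events was a transient rise in systolic pressure of more than 20% from baseline.

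**The case against.** The strongest reply is that the plan does provide a route for these events. Section 14 says heart rate is monitored and all adverse events are recorded at each time point; the Schedule repeats the adverse event review throughout; Section 17 says safety data are gathered before, during and after the intervention. The CRF and the Manual of Procedures are not among the documents and may contain a heart-rate field.

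Much of this stands, and it rules out several stronger readings:
- A reader might infer that these events cannot be ascertained at all. The documents do not support that: VR-arm events can reach the adverse event record through monitoring. What is missing is a scheduled value with which to derive or verify them, and any stated measurement in controls.
- A reader might infer that hypotension alone can be checked from scheduled data. It cannot be checked within the 5-minute window either, because no blood-pressure reading is fixed there.
- A reader might infer a demonstrated bias in a known direction. More complete capture in the VR arm is plausible, but nothing in the documents shows its size or that it will occur.
- A reader might conclude that heart rate should join the mean-change endpoints. That is a preference; event ascertainment does not need it.

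It is also fair to say that part of the imbalance comes from anchoring the event window to VR start, which a heart-rate row alone would leave in place.

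The reply does not close the gap. An adverse event review records what has been recognised, and symptomless threshold events are recognised by measurement. For controls, no such measurement is specified.

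**Conclusion.** The point holds as an internal inconsistency that affects the primary endpoint. Three of four named cardiac events depend on a variable with no scheduled reading in either arm and no stated measurement in controls. The primary proportion can therefore be ascertained unequally, and each participant affected is worth 6.7 percentage points in an arm of 15.

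This assumes that the Schedule governs what is recorded, that the unseen CRF does not already capture heart rate in both arms, and that events are counted per participant. If the CRF does capture it in both arms, what remains is to align the Schedule and resolve the timing and anchor questions. It should be corrected, but it does not make the endpoint unusable.

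**What to change.** - Reconcile Section 14 with the Schedule: record heart rate with the existing SpO2, respiratory rate and blood-pressure readings at Times 1, 2 and 3, in both arms, and give it a CRF field.
- State the time anchor for Times 1 to 3 in controls.
- Reconcile the 5-minute event window with the pre, 10-minute and post readings, and say how the window applies to participants who have no VR start.
- State how the arrhythmia item is ascertained in each arm. A heart-rate value alone does not separate supraventricular from ventricular rhythm.
- Say which variables the 20% criterion covers.

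The cost is one Schedule row, one CRF field if none exists, and a short paragraph on timing and anchors. No new visit is needed, because the other vital signs are already scheduled at these times. The main practical burden is in the control arm, where readings now described as usual care would have to be taken and recorded at defined times.
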